2.3.1. Description of Randomization and Study Arms

Randomization will be conducted at the level of the cluster (1 cluster = 1 health facility). We will randomize 15 clusters evenly to one of three arms: (1) standard of care; (2) optimized standard of care (optimized with support for delivery of standard of care services including support for staff training, job aids, and quality of service delivery); or (3) group HIV self-testing. All patients enrolled at the site will follow the HIV testing assignment for the cluster in which they are randomized. We will use block randomization, blocking on variables that might predict outcomes, including facility type (hospital/health center), location (rural/urban), region (central or southern), and whether facilities have separate or combined STI and OPD clinics. This will help minimize residual confounding that can result in cluster randomized trials. We will then randomly allocate one cluster from each block to each of the three study arms. Clusters will be randomized to achieve a 1:1:1 allocation to each study arm.

Description of Study Arms

Microsoft Excel will be used to randomly assign clusters. Clusters will be assigned to one of three arms:

1. Standard of care arm: Facilities randomized to the standard of care arm will continue with standard of care without any intervention from the study team. Provider-initiated-testing-and-counseling (PITC) is standard of care for both OPD and STI clients. OPD or STI providers tell patients about HIV testing and refer them to the standard HIV testing services room at the health facility. HIV testing activities completed under standard of care will vary by facility based on adherence to national guidelines for PITC.
2. Optimized standard of care arm: Facilities randomized to the optimized standard of care arm will perform PITC for OPD and STI clients as per Ministry of Health National Guidelines. Facilities will be supported by the study team with initial trainings on the importance of HIV testing, the role of HIV testing as part of outpatient and STI care, and strategies used to discuss HIV testing with patients. The study team will also provide job aids to remind providers about the importance of referring patients for HIV testing and assist in the monitoring and evaluation of PITC implementation. When clients are referred for testing, they will use the standard HIV testing services room located in the same health facility. Testing will be available during all clinic hours and completed by trained HIV Diagnostic Assistants (HDA) who work at the facility (i.e., non-study staff).
3. Group self-testing arm: Facilities randomized to the group self-testing arm will have an HDA provide group education about HIV testing in the waiting areas of OPD and STI clinics. Education will include (1) information about the benefits of HIV testing and treatment, (2) a demonstration of how to use a self-test kit and who should use the kit for testing, and (3) information about follow-up required for both HIV negative (re-testing at regular intervals) and positive results (referral for confirmatory testing and ART initiation and follow-up). Self-test kits will be distributed to eligible clients waiting for OPD or STI services and those who wish to use the kit will be free to do so. Group education and the distribution of self-test kits will take place every several hours to ensure that newly arriving OPD and STI clients are given the opportunity to participate in the study. Completed self-test kits will be anonymous and can be placed in a locked box in the waiting area or given to the standard OPD or STI service provider for interpretation of the result and further counseling. Trained HDAs will also be available in the OPD and STI waiting area in order to answer any questions that arise. Those with a positive self-test who disclose the result to the provider will be referred to undergo confirmatory testing by an HDA using the standard HIV testing services room located in the same health facility.

2.3.2. Recruitment and Enrollment Process

Standard of care arm

Facilities randomized to the standard of care arm will proceed with standard HIV testing within the facility. There will be no study “interventions” at the standard of care sites.

After completing the OPD or STI consultation, clients aged 15 years and older will be asked to participate in a brief 10 minute, anonymized exit survey to assess if they were offered testing, if they were tested, and why they chose to test or not. We will recruit all eligible OPD and STI clients for the survey – including clients who tested and those who did not. Survey participation is completely voluntary and can be refused at any point. Those who self-report as testing HIV positive during OPD or STI services will complete written consent and will provide identifiable information so the study can prospectively track linkage to care.

HIV testing registers, ART registers, OPD registers, and STI registers will be reviewed to measure (1) the number of individuals attending OPD and STI clinics over the study period (denominator), (2) the number of OPD and STI clients tested for HIV (numerator), (3) the proportion of those tested who are identified as HIV-positive (defined as a positive HIV test from two different types of tests – Determine and Uni-Gold), and (4) the proportion of those identified as HIV-positive who linked to ART services. All data will be anonymized from existing registers. Records from OPD and STI clients aged 15 years and older will be included in the study. Over the study period, we will be able to determine the proportion of all STI and OPD patients who receive an HIV test, the proportion of those tested who are HIV-positive, and the proportion of HIV-positive clients who link to ART services. We will also be able to determine differences by age sex, and service type. Because study data will be abstracted from existing clinic records in an anonymized format, no informed consent will be obtained.

Optimized standard of care arm

Facilities randomized to the optimized standard of care arm will provide standard PITC as recommended by the Ministry of Health. Facilities will be supported by the study team to implement standard PITC guidelines. HIV testing services will be available during all clinic hours and completed by trained HIV Diagnostic Assistants (HDA) who work at the site (non-study staff).

After completing the OPD or STI consultation, clients aged 15 years and older will be asked to participate in a brief 10 minute, anonymized exit survey to assess if they were offered testing, if they were tested, and why they chose to test or not. We will recruit all eligible OPD and STI clients for the survey – including clients who tested and those who did not. Survey participation is completely voluntary and can be refused at any point. Those who self-report as testing HIV positive during OPD or STI services will complete written consent and will provide identifiable information so the study can prospectively track linkage to care.

HIV testing registers, ART registers, OPD registers, and STI registers will be reviewed to triangulate the (1) number of individuals attending OPD and STI clinics over the study period (denominator), (2) number of OPD and STI clients tested for HIV (numerator), (3) proportion of those tested who are identified as HIV-positive (defined as a positive HIV test from two different types of tests – Determine and Uni-Gold), and (4) proportion of those identified as HIV-positive who linked to ART services. All data will be anonymized from existing registers. Records from OPD and STI clients aged 15 years and older will be included in the study. Over the study period, we will be able to determine the proportion of all STI and OPD patients who receive an HIV test, the proportion of those tested who are HIV-positive, and the proportion of HIV-positive clients who link to ART services. We will also be able to determine differences by age sex, and service type.

Group self-testing arm

OPD and STI clients in the waiting areas for these clinics will receive a health education talk from a trained HDA while waiting for their clinical consultation. Staff will review the oral consent script explaining that participation in HIV self-testing and study procedures is voluntary and that all data are anonymous. All OPD and STI clients aged 15 years and older will be offered a self-test kit. Those who would like to opt-out will be asked to take a kit and give the unopened kit to the study team during a brief exit survey.

Those who choose to participate in self-testing will be asked to keep the used kit in an opaque bag and give the anonymized self-test kit to the study team during the brief exit survey. The study team will NOT look at the test results, but will staple the opaque bag closed, link the unique identification number on the test bag to the exit survey, and drop the self-test kit into a secure lockbox. Those who do not want to directly give the self-test kit to the study team will be allowed to dispose their test kit in a lockbox located in the waiting area or a lockbox located in the provider consultation room.

After completing the OPD or STI consultation, clients aged 15 years and older will be asked to participate in a brief 15 minute, anonymized exit survey about their experience with self-testing why they chose to use the kit or not. We will recruit all eligible OPD and STI clients for the survey – including clients who used self-testing and those who opted-out of self-testing. Survey participation is completely voluntary and can be refused at any point. Those who self-report as testing HIV positive with a self-test kit will complete written consent and will provide identifiable information so the study can prospectively track linkage to care.

HIV testing registers, ART registers, OPD registers, and STI registers will be reviewed to triangulate the (1) number of individuals attending OPD and STI clinics over the study period (denominator), (2) number of OPD and STI clients tested for HIV (numerator), (3) proportion of those tested who are identified as HIV-positive (defined as a positive HIV test from two different types of tests – Determine and Uni-Gold), and (4) proportion of those identified as HIV-positive who linked to ART services. All data will be anonymized from existing registers. Records from OPD and STI clients aged 15 years and older will be included in the study. Over the study period, we will be able to determine the proportion of all STI and OPD patients who receive an HIV test, the proportion of those tested who are HIV-positive, and the proportion of HIV-positive clients who link to ART services. We will also be able to determine differences by age sex, and service type.

At the end of Aim 1 implementation, focus group discussions will be conducted with providers at participating OPD, STI, and HTC clinics to understand perceptions and acceptability of group self-testing at OPD and STI clinics. All core providers and supporting staff involved with the self-test intervention will be asked to participate (estimated 5 providers and 8 supporting staff at each site). Each site will complete two focus groups; one with providers and one with supporting staff (10 focus groups in total). Only providers over 18 years of age, actively involved in the self-test intervention, and willing and able to consent will participate. Focus groups will last approximately 45 minutes.

2.3.3. Informed Consent

For the group self-testing arm, oral informed consent will be obtained before any study-specific procedures are performed. The informed consent process will include information exchange, detailed discussion, and assessment of understanding of all required elements of informed consent, including the potential risks, benefits, and alternatives to study participation. Oral consent will be gained before being given an HIV self-test kit.

For all arms, oral consent will be obtained before completing a brief, anonymized exit survey about their experience with testing. The informed consent process will include information exchange, detailed discussion, and assessment of understanding of all required elements of informed consent, including the potential risks, benefits, and alternatives to study participation.

For a subset of clients in the self-test arm, oral consent will also be obtained before completing an in-depth interview to gain more information about their experience with and acceptability of self-testing. During the brief exit survey, clients who self-report as (1) testing HIV positive that same day or (2) having not tested but wanting to test for HIV that same day will be taken through written informed consent and identifiable information will be collected to allow the study to track their uptake (linkage) and retention in ART. Identifiable information will NOT be collected for any other client group.

2.3.4. Participant Withdrawal or Termination from the Study

Individuals may withdraw from the study at any time. Participants may also be terminated from the study by the site investigator or designee under the following circumstances:

- Site investigator or designee determines that continued participation in the study would be unsafe or otherwise not in the best interest of the participant
- The study is stopped or canceled by the sponsors, government or regulatory authorities, or site IRBs.

2.4. STUDY PROCEDURES

An overview of the study procedures is provided below. The same data collection processes will be used for ALL study arms.

2.4.1. Standard of Care Arm

2.4.2.1 Standard of Care

Facilities in the standard of care arm will provide routine HIV testing services. No intervention activities will be conducted. HIV testing will follow Ministry of Health National Guidelines using HDAs who will provide individual counseling and serial testing with Determine and Uni-Gold HIV test kits. Discordant results will result in re-testing using the MOH guidelines. Those with positive HIV tests will be counseled and referred to ART services following routine care.

2.4.1.2 Demographic Data Collection

Clients in the optimized standard of care arm who complete an OPD/STI consultation visit will meet briefly with a study staff member after their visit. The study staff member will collect anonymous demographic data including age, gender, highest level of education, and reason for visit to OPD/STI clinic. It will also capture if clients were offered testing, if they were tested, self-reported test result, and why they chose to test or not.

2.4.2.3 Additional Data Collection for those who: (1) test HIV positive that same day; (2) have not tested but want to test for HIV that same day, Participants who self-report as having (1) tested HIV positive that same day or (2) not tested but want to test for HIV

that same day will be asked to complete written consent for collection of identifiable information in order to track linkage and retention to ART.

2.4.2.4 *Registry Data for Triangulation and Linkage*

HIV testing, ART, OPD, and STI registers will be reviewed to measure the number of individuals seen in OPD and STI over the study period, the number tested from OPD and STI clinics, the proportion of those tested who are identified as HIV-positive, and the proportion of those identified as HIV-positive who link to ART services. All data will be anonymized from existing registers. Records from OPD and STI clients aged 15 years and older will be included in the study.

2.4.2. Optimized Standard of Care Arm

2.4.2.1 *Provider Initiated Testing and Counseling (PITC)*

Facilities randomized to the optimized standard of care arm will provide standard PITC as recommended by the Ministry of Health. Facilities will be supported by the study team with initial trainings on the importance of HIV testing, the role of HIV testing as part of outpatient and STI care, and strategies used to discuss HIV testing with patients. The study team will also provide job aids to remind providers about the importance of referring patients for HIV testing and assist in the monitoring and evaluation of PITC implementation. When clients are referred for testing, they will use the standard HIV testing services room located in the same health facility. Testing will be available during all clinic hours and completed by trained HIV Diagnostic Assistants (HDA) who work at the facility (i.e., non-study staff). HIV testing for OPD and STI clients will follow Ministry of Health National Guidelines using HDAs who will provide individual counseling and serial testing with Determine and Uni-Gold HIV test kits. Discordant results will result in re-testing using the MOH guidelines. Those with positive HIV tests will be counseled and referred to ART services following routine care.

2.4.2.2. *Demographic Data Collection*

Clients in the optimized standard of care arm who complete an OPD/STI consultation visit will meet briefly with a study staff member after their visit. The study staff member will collect anonymous demographic data including age, gender, highest level of education, and reason for visit to OPD/STI clinic. It will also capture if clients were offered testing, if they were tested, self-reported test result, and why they chose to test or not.

2.4.2.3 *Additional Data Collection for those who: (1) test HIV positive that same day; (2) have not tested but want to test for HIV that same day, Participants who self-report as having (1) tested HIV positive that same day or (2) not tested but want to test for HIV that same day* will be asked to complete written consent for collection of identifiable information in order to track linkage and retention to ART.

2.4.2.3. *Registry Data for Triangulation and Linkage*

HIV testing, ART, OPD, and STI registers will be reviewed to measure the number of individuals attending the clinics during the period of the study (denominator), the number HIV tested (numerator), the proportion of those tested who are identified as HIV-positive (yield), and the proportion of those identified as HIV positive who link to ART services. All data will be anonymized from existing registers. Records from OPD and STI clients aged 15 years and older will be included in the study. Over the period of the study, we will be able to determine the proportion of all STI and OPD patients who receive an HIV test, the proportion of those tested who are HIV-positive, and the proportion of HIV positive clients who linked to ART services.

2.4.3. Group Self-Testing Arm

A trained study member will meet with clients waiting in the OPD and STI waiting spaces and read the oral consent script explaining that participation in self-testing and study procedures is voluntary. The HDA will then provide group education in the OPD and STI waiting areas about (1) the benefits of HIV testing and treatment, (2) a demonstration of how to use a self-test kit and who should use the kit for testing, and (3) and group counseling about follow-up needed for both HIV negative (re-testing at regular intervals) and positive results (referral for confirmatory testing and ART initiation and follow-up). All individuals 15 years of age and older in the waiting area will be offered a self-test kit.

Clients who tested HIV negative within the past 3 months, previously tested HIV positive, are currently taking ART, are uncomfortable administering the self-test kit, or would like to receive an assisted HIV test either through standard HIV testing protocols or a provider observed HIV self-test kit will be advised to opt-out from the HIV self-test. Those who would like to opt-out for any reason will be asked to take a kit and give the unopened kit to the research team during a brief exit survey.

Those who would like to take the self-test will perform the test while waiting for their appointment. In order to avoid unintended disclosure to participants sitting in the waiting area, after the sample is obtained, individuals will be instructed to put the kit into the opaque testing bag while waiting for the test results in order to ensure privacy and minimize risk of adverse outcomes due to unintended disclosure (approximately 20 minutes). Participants will be allowed to perform the self-test while seated in the waiting area or may move to a more private location on the facility grounds. A private space (tent or other sectioned off area of the waiting area) will be available for individuals who wish to read their test before entering the provider consultation room. After completing the test, participants may do any of the following:

- Individuals who are willing to share the result with the provider will be asked to bring their kit to the provider for interpretation and counseling.
- Individuals will be asked to give the anonymized self-test kit to the study team during the brief exit survey. The study team will NOT look at the test results, but will staple the opaque bag closed, link the unique identification number on the test bag to the exit survey, and drop the self-test kit into a secure lockbox. Those who do not want to directly give the self-test kit to the study team will be allowed to dispose their test kit in a lockbox located in the waiting area or a lockbox located in the provider consultation room.

Trained research assistants and an HDA will be available in the waiting area to answer any questions.

2. *Test Interpretation and Confirmatory Testing*

Participants who test positive with the self-test method and disclose results to the provider will be referred to an HDA to have confirmation testing conducted with routine Ministry of Health testing guidelines. These individuals will receive standard of care counseling by facility HDAs and be referred for ART initiation if their confirmatory HIV test is positive.

2.4.3.4. *Demographic Data Collection*

Participants in the group self-test arm who complete an OPD/STI consultation visit will meet briefly with a study staff member after their visit. The study staff member will collect anonymous demographic data including age, gender, highest level of education, and reason for visit to

OPD/STI clinic. They will also ask whether or not participants performed the HIV self-test, what motivated them to use/not use the self-test, and self-reported test result (if willing to disclose). For those willing, the study staff member will also collect the self-test kit, staple the opaque bag closed (if used), link the unique identification number on the test bag to the exit survey, and drop the self-test kit into a secure lockbox. The study staff member will NOT look at test results.

2.4.3.4 Additional Data Collection for those who: (1) test HIV positive that same day; (2) have not tested but want to test for HIV that same day

Participants who self-report as having (1) tested HIV positive that same day or (2) not tested but want to test for HIV that same day will be asked to complete written consent for collection of identifiable information in order to track linkage other HIV services.

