2.4.4. Post-Intervention Interview

A random subset of 60 OPD/STI clients (30 men and 30 women) in the group self-test arm will be asked to participate in an in-depth qualitative interview. These individuals will be selected from at least three different facilities in the group self-test arm and stratified by sex, use of self-testing (or not), and among those self-reporting a positive self-test result, HIV status. In the interview, participants will be asked about their experience with group self-testing, including concerns about privacy, problems performing or interpreting the test, and any perceived harms or benefits resulting from group self-testing.

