Our secondary outcomes measured will be feasibility and acceptability of group self-testing including privacy concerns, problems with performing or interpreting self-tests, and perceived harms or benefits resulting from self-testing. Qualitative methods (semi-structured in-depth interviews) will be conducted on a subset of individuals (n=40) from the group self-testing arm. Interviews will be translated and transcribed by trained personnel. Interviews will be analyzed in Atlas.ti v.6.2 using thematic analysis. Two investigators will code the first five interviews by themes and compare coding to reach a consensus. A codebook will be developed, and two coders will independently code all transcripts and compare codes to reach a consensus. For each theme, we will describe the range, central tendency, and context in which each theme emerges.

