3.4.4.4 Follow-up Visit of Index Clients

All index clients will be seen by study staff when they come for their next ART follow-up visit. A brief survey will be performed to collect information about whether the client disclosed their HIV status to their sex partner(s), whether they gave self-test kits to their partner(s), and knowledge about whether partners completed the test, knowledge of their partner’s test result, and knowledge about their partner’s linkage to care. We will also survey the index client to determine whether they were able to successfully show their partner(s) how to use the kit and whether any gender-based violence or fear of gender-based violence resulted from use of the self-tests. Index clients who do not return for their ART follow-up visit (more than two weeks late) will be traced through standard site protocols and surveyed either in the community or at the facility, if they return to care.

A random sample of 40 index clients (20 men and 20 women) and 40 index partners (20 men and 20 women) will be selected and asked to participate in semi-structured, in-depth interviews to explore the feasibility and acceptability of providing self-test kits to partners, including challenges with disclosure and questions around harm or perceived risk of harm due to distributing the kits.

2.4.4.5 *Follow-up Visits with Index Partners*

Index partners will be recruited for in-depth interviews through index clients (n=40). During follow-up visits with index clients, a random subset of clients will be given a study invitation card to be given to their sexual partner who was given a self-test kit. The study invitation card will describe the in-depth interview they are being recruited for and provide a study-specific phone number the index partner can call in order to participate in the study. In addition, index clients will be asked if the study team could call the randomly selected partner to discuss the study. Index clients will be told the purpose of the call. If index clients give permission to contact the index partner, up to 2 phone numbers will be collected. Index partners will be called up to 3 times over a 2-week period for recruitment into the study. If the index partner cannot be reached after the third try, the partner will be listed as “unreachable” and excluded from the study.

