Our secondary outcomes measured will be feasibility and acceptability of partner self-testing, privacy concerns, problems with performing or interpreting self-tests, and perceived harms or benefits resulting from self-testing. Qualitative methods (semi-structured in-depth interviews) will be conducted on a subset of index clients ($n=30$) from the partner self-testing arm and 30 from the optimized standard of care arm ($n=30$). Qualitative methods will be the same as those outlined in Aim 1.

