7.3. POTENTIAL RISKS AND DISCOMFORTS

Most study procedures are routine clinical care associated with minimal to no risk in participants. Participation in the group self-testing arm in Aim 1 may feel some psychological stress or discomfort from testing and receiving HIV test results in a public setting. Participation in surveys and qualitative interviews may also cause some psychological stress or discomfort. Participants may decline to participate in the self-testing or decline to answer any questions that make them uncomfortable. Participants in Aim 2 will be screened for risk of intimate partner violence, and those with any risk will be excluded.

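### Aim 1 names distress and unintended disclosure as risks of group self-testing, but lists no survey item for either, so harm can be described but not counted or compared between arms; the interview numbers also conflict

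*Combined protocol and SAP*

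**What the plan says.** **Risks named.** Section 7.3 states that participants in the Aim 1 group self-testing arm "may feel some psychological stress or discomfort from testing and receiving HIV test results in a public setting". Section 2.4.3 has clients place the kit in an opaque bag, partly to "minimize risk of adverse outcomes due to unintended disclosure". The qualitative analysis paragraph of section 2.5.1 lists perceived harms among the secondary outcomes.

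**Exit survey.** In the group self-testing arm the itemised content is demographics, reason for visit, self-reported result if the client is willing, and: "They will also ask whether or not participants performed the HIV self-test, what motivated them to use/not use the self-test". The lists in sections 2.4.1 and 2.4.2 cover demographics, whether testing was offered, whether it was done, the result and the reason. Section 2.3.2 describes the self-testing survey more loosely, as an "anonymized exit survey about their experience with self-testing why they chose to use the kit or not", and section 2.3.3 refers to experience with testing in all arms. The questionnaire is not in the documents.

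**Interviews, Aim 1.** Section 2.4.4 plans interviews on privacy, problems with the test, and perceived harms or benefits, with "A random subset of 60 OPD/STI clients (30 men and 30 women) in the group self-test arm". Section 2.5.1 says that the interviews "will be conducted on a subset of individuals (n=40) from the group self-testing arm". No client in the other two Aim 1 arms is interviewed.

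**Interviews, Aim 2.** Section 3.4.4.4 plans "A random sample of 40 index clients (20 men and 20 women) and 40 index partners (20 men and 20 women". Section 4.2 plans 40 index clients in the optimized standard of care arm. The Aim 2 qualitative analysis paragraph says that interviews "will be conducted on a subset of index clients ($n=30$) from the partner self-testing arm", gives 30 for the optimized arm, and mentions no partners.

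**Safety.** Section 6 (Safety Assessment, Monitoring, and Reporting) is one general sentence, with no event definition, form, timing or reporting path.

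**The concern.** A programme deciding whether to replace or supplement provider-initiated testing with testing in the waiting room needs to know two things about harm: how often it occurs, and whether it is more frequent than under the alternative. The plan reaches up to 5,000 clients per arm with a survey that, as itemised, asks about neither named risk. It leaves harm to a small set of interviews in one arm. Section 2.4 says that the same data collection processes apply in all arms, yet on harm there is nothing to set against the self-testing arm. Most exit-survey clients are anonymous and cannot be asked later.

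The conflicting interview numbers are a separate, smaller matter. They do not cause the gap, since either number leaves it open. But they leave the size of the only planned source of client-reported harm in Aim 1 undefined.

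**Working it through.** **1. The plan's own figure.** Section 2.5.1 gives 5 clusters of 1,000 per arm, intra-cluster correlation (ICC) 0.004, type I error 0.05 (taken as two-sided), coverage of 5%, 10% and 60%, and power of at least 95%. Design effect = 1 + (1,000 − 1) × 0.004 = 4.996, so effective n = 5,000 / 4.996 ≈ 1,001 per arm. Power is 98.9% for 5% vs 10% (96.0% with a t reference on 8 df) and over 99.9% for 10% vs 60%. The statement reproduces, and the harm question does not touch it. The documents give no figure for any harm, so every harm rate below is an assumption.

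**2. What the interviews can exclude (illustration).** With zero reports among n independent interviewees, the one-sided 95% upper bound is 1 − 0.05^(1/n):

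- n = 60: 1 − 0.05^(1/60) = 4.9%
- n = 40: 1 − 0.05^(1/40) = 7.2%

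The chance of meeting at least one case of a harm with an assumed 1% rate is 1 − 0.99^n: 45% for n = 60 and 33% for n = 40. The interviewees are 60/5,000 = 1.2% or 40/5,000 = 0.8% of the arm. The sample is in fact drawn from at least three facilities, stratified by sex and kit use, and includes people who did not self-test, so these bounds show scale only.

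**3. An item asked of all clients.** With full response, effective n ≈ 1,001 per arm and the plan's ICC, the zero-event bound is 1 − 0.05^(1/1,001) ≈ 0.3%. Power by the normal approximation is about 89% for 1% vs 3%, 75% for 2% vs 4% and 45% for 1% vs 2%.

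**4. An item asked only of those tested.** Whether someone learned the result can be asked only of clients who have one. Planned coverage gives 5,000 × 5% = 250, 5,000 × 10% = 500 and 5,000 × 60% = 3,000 testers, or 50, 100 and 600 per cluster.

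| Arm | Design effect | Effective n |
|---|---|---|
| Standard of care | 1 + 49 × 0.004 = 1.196 | 250 / 1.196 ≈ 209 |
| Optimized standard of care | 1 + 99 × 0.004 = 1.396 | 500 / 1.396 ≈ 358 |
| Group self-testing | 1 + 599 × 0.004 = 3.396 | 3,000 / 3.396 ≈ 883 |

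For an assumed 1% in control and 3% with self-testing:

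- Against optimized care: SE = √(0.01 × 0.99/358 + 0.03 × 0.97/883) = 0.00778, z = 0.02/0.00778 = 2.57, power = Φ(2.57 − 1.96) ≈ 73%.
- Against standard care: SE = √(0.01 × 0.99/209 + 0.03 × 0.97/883) = 0.00896, z = 2.23, power = Φ(2.23 − 1.96) ≈ 61%.

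With 10 clusters per comparison, a t reference on 8 df (noncentrality equal to z) lowers the 89%, 73% and 61% to about 80%, 62% and 50%. Within the self-testing arm alone, the zero-event bound is 1 − 0.05^(1/883) ≈ 0.3%.

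**5. Interview numbers side by side.**

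| Group | Procedures text | Analysis text |
|---|---|---|
| Aim 1 self-testing clients | 60 | 40 |
| Aim 2 index clients, self-testing | 40 | 30 |
| Aim 2 index clients, optimized care | 40 | 30 |
| Aim 2 partners | 40 | not mentioned |

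**The case against.** The best defence is that the plan never promised a comparative harm rate. The secondary objective is to assess acceptability, with no comparator, and perceived harms sit inside a qualitative analysis. On that view the interviews do their job, and a rate by arm is a new objective. This stands in part: the gap is an improvement to make, not a failure to deliver a stated comparison. It does not remove the gap, because harm is a named outcome and the protocol accepts a survey harm question elsewhere. The Aim 2 follow-up survey asks index clients in every arm about gender-based violence.

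The survey may also be wider than its summary. The self-testing list comes from a paragraph headed demographic data collection, the survey is elsewhere said to cover experience, and the open question on why a client did or did not test could draw out discomfort. That stands as a limit: an unlisted harm item may exist. None is planned in the text, and no analysis of one is specified. Provider focus groups cover perceptions and acceptability but do not ask clients.

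Two stronger inferences fail. A reader might conclude that no client can be asked later. But clients who report a positive test, or who want to test that day, give written consent and identifying details for tracking. A reader might also expect about 5,000 answers per arm on every new item. A disclosure item reaches only those tested, and comparing testers between arms conditions on something that the intervention changes.

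The plan does mitigate harm: opaque bag, private space, freedom to move and to decline. Those steps reduce risk but do not measure it.

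**Conclusion.** The point holds in a limited form. As written, Aim 1 can describe types of harm from group self-testing but cannot estimate their frequency or compare them between arms, although it names the risks and lists perceived harms as a secondary outcome. A reader might go further and say that the trial cannot show whether group self-testing is harmful. The documents do not support that, since the interviews ask directly about privacy and perceived harms and can reveal individual cases.

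The bounds of 4.9% (60 interviews) and 7.2% (40) assume simple random sampling and no reports. They should not be multiplied up to a count of affected testers, because the interviewees include people who did not self-test. The conclusion about the survey rests on the items listed, not on the questionnaire. The interview-number conflicts are plain contradictions in the current text. Primary power is unaffected. This should be changed because the remedy is cheap, but it does not threaten the main result.

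**What to change.** 1. Add short yes/no items to the existing exit survey in all three arms. Ask every client whether how or where testing was offered caused distress. Optionally ask whether they felt pressured to test; this is my addition, not a harm that the protocol names. Ask those tested whether anyone learned their result without their consent.
2. Report the all-client items by arm with cluster-adjusted intervals.
3. Report the disclosure item mainly as a rate with its interval in the self-testing arm. Label any comparison between arms as descriptive, because it conditions on being tested and the control arms would have only about 250 and 500 testers.
4. If the questionnaire already contains such items, list them in sections 2.4.1 to 2.4.3 and state the analysis in section 2.5.1.
5. Keep the interviews for depth, and state one number per group: 60 or 40 in Aim 1; 40 or 30 index clients in each of the two Aim 2 arms; and whether the 40 partner interviews belong to the analysis.

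The cost is about one more minute in a survey of 10 to 15 minutes and a small analysis addition, with no new staff or visits. Harms that arise after the client leaves the facility would still be missed.
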